Primary Outcome:

- Change from baseline in pain intensity at 12 months. Baseline pain intensity is measured at last CHOIR completion before trial, and is based on patient reported outcome in CHOIR for average pain in the week prior to completion of questionnaire.

Secondary Outcomes:

1. Patient global impression of change at all follow up time points
2. Pain intensity at all follow up time points
3. Change from baseline in function at 12 months
4. Function at all follow up time points
5. Change from baseline in pain interference at 12 months
6. Pain Interference at all follow up time points
7. Change from baseline in depression at 12 months
8. Depression at all follow up time points
9. Change from baseline in anxiety at 12 months
10. Anxiety at all follow up time points
11. Daily opioid dose in morphine equivalent at all follow up time points

Analytic Plan: We will test the hypotheses that:

1. High frequency spinal cord stimulation is more effective than burst spinal cord stimulation in decreasing pain at 12 months in patients with chronic low back and/or leg pain.
2. High frequency spinal cord stimulation is more effective than burst spinal cord stimulation in improving pain, pain interference and function in patients with chronic low back and/or leg pain.

We will use repeated measure linear regression to compare these measures between the groups at follow up time points with time as the fixed effect and treatment as random effect. This method allows missing data subject to assumption of missing at random.

3. Burst spinal cord stimulation is more effective than high frequency spinal cord stimulation in improving depression and anxiety in patients with chronic low back and/or leg pain.

We will use repeated measure linear regression to compare these measures between the groups at follow up time points with time as the fixed effect and treatment as random effect. This method allows missing data subject to assumption of missing at random. Some improvement in depression and anxiety is expected to be the result of improvement in pain and function. We will also perform a stratified analysis in responders (patients who achieve >50% pain relief) and non-responders (patients who do not achieve 50% pain relief) to the treatments.

4. Patients receiving burst spinal cord stimulation will report higher satisfaction with treatment using patient global impression of change compared with patients receiving high frequency spinal cord stimulation.

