We will use SAS Enterprise Guide (SAS Institute Inc., Cary, NC) for all analyses. Our null hypotheses are similarity of measures. We will perform a two-sided hypothesis testing with accepted type I error of 0.05. We will compare baseline characteristics using t-test for continuous variables and chi-square for categorical variables. We will adjust for the variables that are different between the groups in our final regression model. Our primary analysis will be based on modified intention-to-treat. We will only exclude patients with no follow up data from our final analysis. We will then perform a secondary analysis based on implants only (excluding patients who do not achieve appropriate pain control in trial period).

We will then perform the following subgroup analyses:

1. Patients who have undergone lumbar spine fusion versus patients who have not.
2. Patients with back pain only (based on baseline body map) versus patients with back and leg pain or leg pain only.

3. Patients with PROMIS depression measure of above 90th percentile in baseline evaluation.
4. Patients with PROMIS anxiety measure of above 90th percentile in baseline evaluation.

The rate of CHOIR survey completion is more than 60% in our routine clinical care. We expect a higher rate for our proposed study considering that these surveys are abbreviated, and participants will receive more frequent reminders as well as telephone reminders (currently patients receive only one email reminder to complete the survey). For our primary outcome we will try to minimize missing data by calling the patients who do not complete the surveys up to seven times; we will try to ask and record the pain intensity even if they are not willing to complete surveys. Our analysis model will allow for missing data in longitudinal variables, subject to assumption of missing at random.

Data and Safety Monitoring Plan: We will not perform any interim analyses for benefit, harm or futility. We will establish a data and safety monitoring board consisting of investigators, at least two independent clinicians in our clinic (not part of the study team), and at least one neurosurgeon subspecialized in spine surgery who will monitor the study quarterly for adverse events and patient safety, reporting of adverse events, enrollment pace and study timeline, quality of data, and deviations from the protocol.

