Sample size: The highest standard deviation of NRS pain scale in our clinic is 2.25 based on prior publications.^{19,21-25} Accepting type I error of 0.05 with 80% power, we will require 80 participants per group to detect one unit between-group difference in change from baseline in NRS pain scale. We are proposing a more conservative (larger) sample size to preserve power considering that some patients do not proceed from trial to implant and do not receive therapy. Currently more than 80% of patients who undergo a trial of spinal cord stimulation proceed to receiving an implant. We will therefore target 100 patients in each arm. Correlation between repeated measure will decrease variance and increase the power of the proposed study.

Timeline: Stanford Pain Management Center performed more than 120 trial of spinal cord stimulation in 2017 and this practice is increasing in our division. We expect a high consent rate considering the nature of our study. We believe we will be able to complete recruitment in two years; thus, last follow up of last recruited patient will be completed by five years.

Data Management: CHOIR will be the main tool for data collection and storage for the study. At completion of the study, the data from CHOIR, participants' electronic health records and California Prescription Drug Monitoring Program will be downloaded for analysis. After initial steps of data preparation, we will de-identify the dataset for further analysis. The principal investigator will save the de-identification code on a secure computer within Stanford University Network only.

Limitations:

1. One of the most important advantages of pragmatic clinical trial with less stringent inclusion/exclusion criteria is to improve the ability to generalize the results to a wider range of patients. However, considering that the current study is a single center study conducted in a tertiary pain management center, our sample might not be representative of chronic pain patients seen by community pain providers.
2. Our aim is to integrate our trial into patient care; thus, we are not blinding the provider and the participants. Method of data collection is similar in both groups and does not involve interaction with investigators. This will minimize, but not eliminate, the bias introduced by proceeding with an open label design.

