Appendix 3. Measurement tools (not including PROMIS item banks)

Patient Global Impression of Change (PGIC)

Since the start of the study, my overall status is:

- Very Much Improved
- Much Improved
- Minimally Improved
- No Change
- Minimally Worse
- Much Worse
- Very Much Worse

Pain Intensity:

In the past 7 days:

How intense was your average pain on a scale of 0-10 with zero indicating no pain and 10 indicating the worst imaginable pain?

In the past 7 days:

How intense was your pain at its worst on a scale of 0-10 with zero indicating no pain and 10 indicating the worst imaginable pain?

References

1. Relieving Pain in America: A Blueprint for Transforming Prevention, Care, Education, and Research. Washington (DC), Institute of Medicine, 2011

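### The fallback call names only pain intensity, so PGIC, hypothesis 4's one-question endpoint, is missing at that visit for patients who give a pain score but still decline the survey

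*Combined protocol and SAP*

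**What the plan says.** All references are to the combined protocol and SAP, section (c) Approach, and its Appendix 3.

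- **Data Collection.** PGIC, on a seven-point scale, is part of the electronic survey emailed at 1, 3, 6, 12, 18, 24 and 36 months. Patients who have not responded within seven days are contacted with a reminder. No other way of obtaining PGIC is described.
- **Outcomes.** The first secondary outcome is "Patient global impression of change at all follow up time points".
- **Analytic Plan, hypothesis 4.** Burst is expected to do better than high frequency on PGIC. No other endpoint is attached to this hypothesis, and no model is named for it.
- **Analytic Plan, survey completion.** "The rate of CHOIR survey completion is more than 60% in our routine clinical care". A higher rate is expected in the study because the surveys are shorter and reminders more frequent, but no figure is given. To protect the primary outcome, non-completers are called up to seven times, and "we will try to ask and record the pain intensity even if they are not willing to complete surveys". Remaining gaps in longitudinal variables are left to a model that assumes missing at random.
- **Analytic Plan, analysis set.** The modified intention-to-treat set leaves out only patients with no follow-up data.
- **Appendix 3.** PGIC is a single stem, "Since the start of the study, my overall status is", with seven response options.

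**The concern.** The call will already have reached a patient who is prepared to answer a short question. Pain on a 0-10 scale is asked; PGIC, which is no longer, is not listed. The plan thus gives up data on a hypothesis-bearing endpoint that it could collect in the same conversation, and a PGIC answer not asked for at a visit cannot be obtained afterwards.

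Two features make PGIC the natural item to add. It has no baseline value, so a patient who supplies pain only by telephone and never completes a survey stays in the modified intention-to-treat set, counts towards the pain hypothesis, and contributes no PGIC at all. And the hypotheses point in opposite directions: high frequency is expected to win on pain, burst on PGIC. If the results diverge in that way, a reader will want to know that the contrast does not partly reflect who answered which question. Patients who decline surveys may differ in global impression from those who complete them, and in an open-label trial that difference need not be the same in both arms.

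**Working it through.** **1. The plan's own figure.** Inputs from the Sample size paragraph and Analytic Plan: "Accepting type I error of 0.05 with 80% power", "two-sided hypothesis testing", a difference of 1 NRS unit, and an SD of 2.25 ("The highest standard deviation of NRS pain scale in our clinic is 2.25 based on prior publications").

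n per group = 2 × (1.960 + 0.842)² × 2.25² / 1² = 2 × 7.849 × 5.0625 = 79.5, rounded up to 80. Then 80 / 0.80 = 100 per arm.

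Both stated figures reproduce. The step from 80 to 100 is justified by patients who do not go from trial to implant. It reserves nothing for missing surveys, and no effect size, SD or power is given for PGIC.

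**2. Which patients are affected.** The text yields three groups at a visit where calls are made:

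| Patient | Pain score | PGIC |
|---|---|---|
| Completes the survey, with or without a reminder or call | yes | yes |
| Reached, declines the survey, gives a pain score | yes | no |
| Not reached, or declines everything | no | no |

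The point concerns the middle row only.

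**3. Illustration of size.** Let c be the survey completion rate after all reminders and r the share of remaining non-completers who answer the fallback question. Neither is fixed by the documents: 60% is a routine-care floor, 80% is assumed for contrast, and r = 0.5 is assumed. With 100 per arm:

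- PGIC available as written: 100 × c
- PGIC available if asked on the call: 100 × [c + (1 − c) × r]
- Excess standard error at a single visit relative to complete data: √(100/n) − 1

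| c | n as written | Excess SE | n with PGIC on the call | Excess SE |
|---|---|---|---|---|
| 60% | 60 | √(100/60) − 1 = 29% | 60 + 40 × 0.5 = 80 | √(100/80) − 1 = 12% |
| 80% | 80 | √(100/80) − 1 = 12% | 80 + 20 × 0.5 = 90 | √(100/90) − 1 = 5% |

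**4. Sensitivity to r.** At c = 60%, r of 25%, 50% or 75% gives 70, 80 or 90 per arm. At c = 80% it gives 85, 90 or 95.

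**5. The same in detectable difference.** (1.960 + 0.842) × √(2/n) gives 0.51 SD at n = 60, 0.44 SD at n = 80 and 0.42 SD at n = 90. If one borrows 1/2.25 = 0.44 SD from the pain calculation as a stand-in effect for PGIC (an assumption), power goes from 68% to 80% in the first row of the table in step 3 and from 80% to 85% in the second.

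These are single-visit figures. A longitudinal model using a patient's other PGIC answers would reduce the loss for anyone who completes some surveys.

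**The case against.** The best defence is that this is deliberate. The calls are introduced as a measure for the primary outcome, and limiting a request to people who have just refused a survey to the one value that matters most is reasonable. That stands: nothing in the plan contradicts itself here. It does not, however, conflict with asking one more question once pain has been recorded.

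Several stronger readings are tempting and are not supported.

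- *A reader might infer that PGIC is lost for everyone reached by telephone.* The contact is first a reminder, and those it prompts to complete the survey supply PGIC.
- *A reader might infer that the plan rules PGIC out of the call.* It is silent; it names pain and does not forbid anything else.
- *A reader might take 40 missing per arm, or a 29% larger standard error, as the expected loss.* The 60% is a floor from routine care with a single email reminder, and the plan expects to exceed it.
- *A reader might infer that hypotheses 1 and 4 would be tested in separate populations.* PGIC is collected at seven visits, and a missed survey at one of them need not remove a patient from a longitudinal analysis under missing at random. That assumption does not, though, restore unasked answers.

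Two further objections bear on the remedy. Because the primary outcome is pain at 12 months, the calls may be meant for that visit alone, in which case the gain is confined to it. And Limitations, item 2, relies on data being collected without contact with investigators to contain open-label bias. Asking a second subjective item by telephone widens an exception that the plan already makes for pain.

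**Conclusion.** The point holds in a limited form. Followed as written, the plan leaves PGIC missing at a visit for patients who are reached, will not complete the survey, and do give a pain score. It is an avoidable loss on a secondary endpoint that carries its own hypothesis. It is not an error, and it leaves the primary analysis untouched.

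Its size is unknown. The illustrative gain is 20 patients per arm at 60% completion and 10 per arm at 80%, both resting on the assumption that half of non-completers would answer by telephone; higher completion or a lower answer rate shrinks it. Whether bias is also reduced depends on how survey-decliners differ from completers, about which the documents say nothing. This is a cheap improvement worth making before calls begin, and not a condition for the trial's validity.

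**What to change.** In the survey-completion paragraph of the Analytic Plan:

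1. State that the fallback call asks average pain first, so that the primary outcome is secured, and then the one-item PGIC with the Appendix 3 wording.
2. Say at which visits the call is made, 12 months at the least, and ask both items whenever it is made.
3. Record mode of collection (web or telephone) for both items.
4. Add a sensitivity analysis repeating the PGIC comparison with web responses only.
5. Have the call scripted and made by staff other than the treating investigators, and amend Limitations, item 2, to acknowledge telephone collection.

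The cost is one extra question in calls already planned, one flag variable and one additional analysis. The real downside is that some PGIC answers will come from a conversation with study staff in an open-label trial. The script, the choice of caller and the web-only analysis limit that risk but do not remove it.

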Randomization: After obtaining informed consent, the patients who meet the inclusion and exclusion criteria will be 1:1 randomized to undergoing treatment with spinal cord stimulation with either high frequency or burst waveforms. Treating pain physician will randomize the patient during clinic visit using CHOIR point-of-care randomization system. Randomization algorithm will be based on computer generated numbers in random blocks of four, six and eight.

Blinding: Two different competing manufacturing companies will be providing devices that deliver these two waveforms. Interacting with the manufacturer representative for programming and device maintenance will inform the patient of the type of waveform. Therefore, blinding will be challenging, and we will not attempt to blind the patients to the treatment they are receiving. The risk profile and maintenance of these devices are similar; they are novel to the patients with similar efficacy literature. Thus, we do not expect differences in either compliance or therapy expectation secondary to lack of blinding. The figure shows the process of the study up to randomization.

Intervention: At Stanford Pain Management Center, pain physicians identify candidates for spinal cord stimulation; thereafter, they refer these patients to our pain psychologists. A multidisciplinary neuromodulation team conference – which is attended by pain physicians and pain psychologists in our division – assesses appropriateness of spinal cord stimulation for these candidates based on their pain diagnosis, spinal anatomy, history of spine surgery, medical comorbidities, psychological comorbidities, expectations, cognitive status and mood stability. The team also recommends the choice of devices appropriate for each patient who is identified as an optimized candidate. With current evidence, the team does not distinguish between high frequency and burst waveforms. The checklist of items discussed during these team conferences is provided in Appendix 1. The treating physician will then obtain informed consent and randomize the patients who are identified as optimized candidates for spinal cord stimulation by multidisciplinary neuromodulation team conference. These participants will receive treatment with either high frequency or burst spinal cord stimulation.

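### The 80-per-arm figure uses the SD of a pain score as the SD of its 12-month change, which for unadjusted change scores implicitly assumes a baseline to month-12 correlation of 0.5

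*Combined protocol and SAP*

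**What the plan says.** The primary outcome (Outcomes) is "Change from baseline in pain intensity at 12 months", based on average NRS pain over the past week, with baseline taken from the last registry survey before the stimulation trial. Allocation is 1:1.

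The Sample size paragraph gives one SD: "The highest standard deviation of NRS pain scale in our clinic is 2.25 based on prior publications". It continues: "Accepting type I error of 0.05 with 80% power, we will require 80 participants per group". The effect that this number is meant to detect is a gap of one NRS point between the arms in their change since baseline. It raises 80 to 100 per arm because some patients do not go on from trial to implant, citing an implant rate above 80%. It closes with: "Correlation between repeated measure will decrease variance and increase the power of the proposed study".

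The Analytic Plan sets the test: "We will perform a two-sided hypothesis testing with accepted type I error of 0.05". The model is a repeated-measures linear regression at the follow-up time points, with time and treatment as its named effects. Baseline pain is not named in it. Covariates enter only if they are found to differ between the groups. The primary set is modified intention-to-treat and leaves out only patients without any follow-up data, so failed trials stay in.

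Neither an SD of the 12-month change nor a correlation between baseline and month-12 pain is given anywhere.

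**The concern.** The SD of a score and the SD of a change in that score are different quantities, linked by the correlation between the two measurements. The paragraph describes the first and uses it for a difference in the second without saying what correlation makes them equal. It then offers correlation as a further source of power. If the calculation is meant for unadjusted change scores, a correlation of 0.5 has already been spent in reaching 80 per group. Only correlation above 0.5 adds anything, and correlation below it costs power.

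At stake is the power statement for the primary outcome. Under an unadjusted change-score comparison, 80 per arm could give anything from about 60% to about 88% power over a range of correlations that the documents do not narrow.

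**Working it through.** **Inputs from the documents.** SD 2.25, difference 1 unit, two-sided alpha 0.05, power 80%, 1:1 allocation, implant rate 80%, target 100 per arm. **Assumed:** rho, the baseline to month-12 correlation, shown as a range.

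**Step 1: reproduce the plan's figures.**
n per arm = 2 × (1.960 + 0.842)² × 2.25² / 1² = 79.5, so 80. An exact t-test calculation gives 80.4, with power 79.8% at 80 per arm. A one-sided test would give 63, which does not match. The target follows as 80 / 0.8 = 100. The value 2.25 was therefore entered unchanged as the SD of change.

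**Step 2: what that implies.**
With the same SD at both times, SD(change) = 2.25 × √(2(1 − rho)). This equals 2.25 when 2(1 − rho) = 1, that is, at rho = 0.5.

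**Step 3: unadjusted change score over a range of rho.** Required n uses the formula in step 1. Power uses the noncentral t distribution with an undiluted one-unit effect.

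| rho | SD of change | n per arm for 80% | Power, 80 per arm | Power, 100 per arm |
|---|---|---|---|---|
| 0.2 | 2.85 | 128 | 60% | 70% |
| 0.3 | 2.66 | 112 | 66% | 75% |
| 0.4 | 2.46 | 96 | 72% | 81% |
| 0.5 | 2.25 | 80 | 80% | 88% |
| 0.6 | 2.01 | 64 | 88% | 94% |

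The normal approximation gives values up to one percentage point higher (for example 73% and 82% at rho 0.4).

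**Step 4: how far the 0.5 moves.**
- With all 100 per arm analysed and the full effect, the largest SD that keeps 80% power is 1 / (2.802 × √(2/100)) = 2.52. Break-even is then rho = 1 − 2.524² / (2 × 2.25²) = 0.37.
- With 80 per arm and SDs b at baseline and f at month 12, break-even is rho = (b² + f² − 2.25²) / (2bf). Both SDs 2.0 gives 0.37; 2.0 and 2.25 gives 0.44; 2.25 and 2.5 gives 0.56. These SDs are illustrations.

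**Step 5: is the margin to 100 a reserve?**
Failed trials stay in the primary set. If, as an illustration, 20% without an implant dilute the effect to 0.8 units, power at 100 per arm is 71% at rho 0.5 (SD 2.25) and 56% at rho 0.3 (SD 2.66).

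**Step 6: baseline-adjusted comparison.**
If 2.25 is the month-12 SD, the residual SD is 2.25 × √(1 − rho²), which never exceeds 2.25. At 80 per arm with the full effect:
- rho 0: SD 2.25, power about 80%
- rho 0.3: SD 2.15, power 83%
- rho 0.5: SD 1.95, power 90%

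**The case against.** The arithmetic in the plan is correct, and the planned model is not a t-test on change scores. It compares measures at the follow-up time points. Under randomisation, a comparison of month-12 scores estimates the same between-group difference, and a score SD is then the right kind of SD at any correlation. 2.25 is also the highest of several published values, and the target is 100 per arm rather than 80.

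Much of this stands, and it rules out several stronger readings that a reader might infer:

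- *That 80% power holds only if rho is at least 0.5.* That threshold needs an unadjusted change score, an SD of exactly 2.25 at both times and 80 patients analysed per arm, all together. The documents fix none of these clearly. There is no such threshold for a raw month-12 comparison or with baseline adjustment.
- *That calling 2.25 the highest SD is falsely conservative.* It is conservative relative to the other values cited. Whether it is large enough for a change score depends on a correlation that is not given.
- *That the correlation must be low because many patients are expected to lose more than half of their pain.* Responder rates do not determine rho, and uneven response would also alter the month-12 SD.
- *That the correlation sentence is simply wrong.* It can be valid for a baseline-adjusted model or for an analysis that uses several follow-up visits. With equal variances, an average of visits never varies more than a single visit.

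What the objection does not remove is the gap itself. The outcome and the stated effect are both changes from baseline, the SD is not, and the Analytic Plan brings baseline pain into the model only if it happens to differ between the groups. The margin to 100 is real, but the plan assigns it to patients who do not reach implant.

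**Conclusion.** The point holds as an undeclared planning assumption, not as a computational error. If change scores are compared without baseline adjustment, with an SD of 2.25 at both times, the 80-per-group figure builds in rho = 0.5. At 80 per arm power would then be 72% at rho 0.4, 66% at 0.3 and 60% at 0.2. If all 100 per arm are analysed with an undiluted effect, break-even falls to about 0.37. The unconditional claim of extra power from correlation is not supported for that analysis unless rho exceeds 0.5.

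The documents do not show that the trial is underpowered, because they give neither the correlation nor the SD of change and leave open how baseline pain enters the primary model. The point concerns the power statement. It does not imply bias in the treatment estimate or a raised type I error.

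**What to change.** **Preferred.** In the Analytic Plan, name baseline NRS pain as a covariate in the primary model, regardless of any observed imbalance. In the Sample size paragraph, state that 2.25 is taken as the month-12 SD and restate the power for the baseline-adjusted comparison, using the figures in step 6. The 80% at 80 per arm then holds at any correlation, provided that the month-12 SD is no larger than 2.25 and the effect is the full one unit. Dilution from failed trials remains a separate matter.

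**Alternative.** If unadjusted change scores are kept, quote the SD of the 12-month change, or rho with the month-12 SD, from existing CHOIR data, and restate the power at 100 per arm.

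**Either way.** Keep the correlation sentence but qualify it: the gain applies to the baseline-adjusted or repeated-measures analysis.

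**Cost.** The preferred route changes wording only. Baseline pain is already collected, and no patients are added. The alternative needs one query of the existing registry, and the restated power may be less favourable than 80%.

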High Frequency: After randomization, the patient will be scheduled for placement of trial system. We will use Senza® (Nevro Corp., Palo Alto, CA) trial and implant systems to deliver high frequency spinal cord stimulation. A trial system includes two trial leads, an external pulse generator, and a remote control. The permanent implant system includes two leads, an internal pulse generator, a remote control, and a charging device for internal pulse generator. We will use our routine process of trial and implant.

We will position the patients prone on the operating room table, minimizing the lordosis of lumbar spine. We will assist patient comfort and relaxation by nurse-administered moderate sedation titrating doses of midazolam and fentanyl. The patients will be conversing to communicate unusual pain to avoid accidental damage to any neural structures. After

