The trial and implant process will be identical to high frequency with one difference: correct placement of the leads will be confirmed during the trial procedure by inducing paresthesia over the painful area (instead of standard anatomical placement with high frequency). The parameters of the stimulation are as below: each burst includes 5 pulses of electrical stimulation at intra-burst frequency of 500 hertz without time for discharge in between pulses. These bursts will be repeated at inter-burst frequency of 40-60 hertz. The amplitude will range between 0 and 15 milliamperes.

Data Collection: As a part of evaluation for spinal cord stimulation, patients in our clinic complete initial survey on Collaborative Health Outcomes Information Registry (CHOIR). The participants will receive electronic surveys via email at 1, 3, 6, 12, 18, 24 and 36 months after the operation for implant of spinal cord stimulator (or trial in case of failed trial). The participants will receive email reminders after three and five days if the surveys are not completed. If the participants do not complete the surveys within seven days of receipt of the survey link, they will be contacted to be reminded of the survey. These surveys will include average and worst Numerical Rating Scale (NRS) of pain; National Institute of Health (NIH) Patient Reported Outcomes Measurement Information System (PROMIS) measures for function, pain interference, depression and anxiety; patient global impression of change on a 7-point Likert scale; and questions about any adverse events related or unrelated to the therapy. Data about use of other analgesics and medications, and pain interventions

will also be recorded at these intervals from participants' electronic health records and California Prescription Drug Monitoring Program. We will also record participants' baseline characteristics including age, sex, main pain diagnosis, other pain diagnoses, psychological comorbidities, medical comorbidities, medication use, and education level.

Adverse events will be reported to the principal investigator either directly by the participants or through the treating pain physician at Stanford Pain management Center. The principal investigator is responsible for reporting the adverse events and deviations from the protocol appropriately to institutional review board and other authorities.

Mood instability will be monitored as a component of routine clinical care by treating physician.

Outcomes:

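### The stated reason for raising 80 to 100 per arm fits the secondary implants-only analysis, not the primary modified intention-to-treat analysis, so 80% power for the primary comparison is not demonstrated (nor shown to be missed)

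*Combined protocol and SAP*

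**What the plan says.** The Sample size paragraph of the combined protocol and SAP starts from one input on variability: "The highest standard deviation of NRS pain scale in our clinic is 2.25". With a type I error of 0.05 and 80% power it concludes that "we will require 80 participants per group to detect one unit between-group difference in change from baseline in NRS pain scale". It then enlarges the target: "We are proposing a more conservative (larger) sample size to preserve power considering that some patients do not proceed from trial to implant". The rate behind the enlargement is "Currently more than 80% of patients who undergo a trial of spinal cord stimulation proceed to receiving an implant", and the target becomes 100 per arm. The paragraph closes with "Correlation between repeated measure will decrease variance and increase the power of the proposed study", and gives no correlation.

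Three other places decide who is in the primary analysis:

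- **Intervention (High Frequency and Burst):** "After randomization, the patient will be scheduled for placement of trial system". Randomisation therefore precedes the trial period.
- **Data Collection:** surveys are timed "after the operation for implant of spinal cord stimulator (or trial in case of failed trial". Patients whose trial fails are followed on the same schedule.
- **Analytic Plan:** the primary analysis is mITT, and "We will only exclude patients with no follow up data from our final analysis". An implants-only analysis is secondary.

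The Analytic Plan also reports routine survey completion of more than 60% and expects a higher, unquantified rate in the study. It plans up to seven calls to obtain the pain score and relies on a missing-at-random model. Covariates enter the final regression only if they are found to differ between groups.

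**The concern.** Dividing by 0.80 is the correction for patients who drop out of an analysis set. Patients with a failed trial do not drop out of the primary set. Their possible effect on mITT power is dilution of the treatment difference, and that calls for division by the square of the implanted fraction. Whether there is any dilution depends on the population in which the 1 unit is expected, which the plan does not state.

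One group does leave the primary set in the way that 1/(1 − d) assumes: patients randomised but never trialled, or not implanted after a successful trial. They have no stated survey start and may have no follow-up data. The rate of more than 80% is conditional on having had a trial, so it does not count the never-trialled, and no figure for this group is given.

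Readers will take 100 per arm as securing at least 80% power for the primary comparison. No interim analysis is planned, so this paragraph is their only guide to how informative a null result would be.

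**Working it through.** **Inputs.** From Sample size: SD 2.25, difference 1 unit, power 80%, implant rate above 80%, target 100 per arm. From the Analytic Plan: two-sided 0.05, mITT primary. From Randomization: 1:1 allocation. Assumed here because the plan gives no figure: implant rates of 80%, 85% and 90%; 12-month completion of 80% and 90%; baseline to 12-month correlation r; equal variances at the two visits. Power figures are for a two-sample t-test.

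**Step 1. Reproduce the plan.**
n = 2(1.96 + 0.8416)² × 2.25² / 1² = 79.5, or 80 per arm (80.4 with the t distribution).
80 / 0.80 = 100. The plan does not write out this division, but the result is exact.

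**Step 2. Which set does the division serve?** Implants-only: 100 × 0.80 = 80 per arm, giving 80% power for 1 unit with complete data. In mITT, patients with a failed trial remain, so the division does not describe what happens to that set.

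**Step 3. If the 1 unit is for all randomised patients.** Failed trials need no inflation. The extra 20 then works as a missing-data allowance.

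| 12-month scores available per arm | Power, difference 1.0, SD 2.25 |
|---|---|
| 100 | 88% |
| 90 | 84% |
| 80 | 80% |

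**Step 4. If the 1 unit is for implanted patients only.** Assume no arm difference in the others and equal implant rates p. The mITT difference is then p × 1, and the required n is about 80 / p². At p = 0.80 this is 80 / 0.64 = 125.

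| Implanted | mITT difference | n per arm for 80% power | Power at 100 per arm, complete data |
|---|---|---|---|
| 80% | 0.80 | 125 | 71% |
| 85% | 0.85 | 111 | 76% |
| 90% | 0.90 | 99 | 80% |

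At 80% implanted, with 90 or 80 scores per arm, power is 66% or 61% at SD 2.25. A repeated-measures model that borrows from other visits would do somewhat better.

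**Step 5. Dependence on the SD.** The 2.25 is given for the pain score and is used for the change in score.
SD of change = 2.25 × √(2(1 − r)), which equals 2.25 only at r = 0.5. At r = 0.3 it is 2.66, and power at 100 per arm with complete data falls to 75% for a 1.0 difference and 56% for 0.8. In the other direction, the largest SD of change that keeps 80% power at 100 per arm is 2.51 for a 1.0 difference (r about 0.38) and 2.01 for 0.8 (r about 0.60).

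**Step 6. Baseline pain as a covariate.** Adjusted SD = 2.25 × √(1 − r²), which is 1.949 at r = 0.5 and 2.146 at r = 0.3.

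| Difference | r | Plain change score | Adjusted for baseline |
|---|---|---|---|
| 0.8 | 0.5 | 71% | 82% |
| 0.8 | 0.3 | 56% | 75% |
| 1.0 | 0.5 | 88% | 95% |
| 1.0 | 0.3 | 75% | 91% |

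These are powers at 100 per arm with complete data.

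**The case against.** The strongest reply is that the number may be perfectly adequate. Both 80 and 100 reproduce. If the 1 unit is meant for all randomised patients, 100 per arm is ample with complete data and still gives about 80% with a fifth of the 12-month scores missing. The plan took the highest SD among several publications, its implant and completion rates are stated as floors, and telephone capture of the pain score should limit losses. The 71% rests on assumptions that no section supports: equal implant rates, and no arm difference among patients who are not implanted. Unequal implant rates could move the mITT difference either way. The planned analysis is a repeated-measures model, not a t-test.

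All of this stands, and it limits the point. A reader might infer that the trial is underpowered, or that on the implanted-only reading 80% power needs about 90% implanted. The documents support neither. The 90% figure holds only at an SD of change of 2.25; at r of about 0.60, or with baseline adjustment at r = 0.5, a 0.8 difference reaches 80% or more with only 80% implanted. The 66% and 61% are not floors either, because an SD of change above 2.25 would lower them.

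The reply does not supply the missing statements. The adequate case uses a population and a loss allowance that the plan does not state, and the choice of the highest SD concerns scores, not changes. The closing sentence on correlation gives no value, so no gain can be credited to it.

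It may also be said that the covariate is a separate matter. It does change the primary model. It is raised here because it offers a definable gain in place of that unquantified sentence.

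**Conclusion.** The point holds as a gap in the justification, and should be fixed. The only stated reason for the extra 20 per arm matches the secondary implants-only set. The population for the 1 unit is not named, and missing 12-month scores have no place in the calculation. Power for the primary analysis with complete data and an SD of change of 2.25 is 88% on one reading and 71% to 80% on the other (80% to 90% implanted, equal implant rates, no difference in the non-implanted). Which applies cannot be determined from the documents. The 80% target is not demonstrated for mITT; it is not shown to be missed.

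**What to change.** No change in N.

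1. In Sample size, state whether the 1 unit is the difference in all randomised or in implanted patients. Restate the mITT power with the assumed implant rate, 12-month pain-score completion, share with no follow-up data (including patients never trialled, or not implanted after a successful trial) and SD of change.
2. Give the extra 20 per arm a reason that matches. If all randomised: it covers up to 20% without a 12-month score. If implanted only: say that 100 per arm gives about 71% to 80% mITT power at 80% to 90% implanted with complete data, and 80% for the implants-only analysis.
3. Prespecify baseline pain as a covariate in the primary model whether or not it differs between arms. This replaces, for that variable, the Analytic Plan's rule of adjusting only for observed differences, and it should take the place of the closing sentence on correlation.

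The cost is a reworded paragraph and one covariate that is already collected, with no added patients, visits or data. If the 1 unit was meant for implanted patients, the stated power becomes less favourable.
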